THC, the primary psychoactive ingredient of marijuana, is known to impair short-term memory, increase reaction time and impair attention. We will examine four tasks sensitive to the effects of THC using a simple app in a controlled setting (memory task, motor tapping task, reaction time and addition; Broyd et al, 2016; Desrosiers et al, 2015). The data obtained in the controlled setting will provide the basis for future testing in the naturalistic, field setting. Fifty-six healthy experienced but non-daily marijuana users will be recruited for a three-session laboratory study, in which they receive oral doses of THC (7.5 and 15 mg oral) and placebo under double blind conditions. They will be required to be THC-free at the beginning of the 4-hour sessions. During the sessions subjects will ingest the drugs and complete the app tasks two hours after ingestion, as well as standardized laboratory measures of performance and mood states at half hour intervals. Subjects will be asked to estimate their level of performance before and after each app task completion, without feedback on their actual performance. Cardiovascular measures (heart rate and blood pressure) will be obtained at regular intervals. The primary goal is to develop app tasks that are sensitive to the drug's effects and the drug dose on performance, as a model for future field testing.

We would like to expand on several methodological considerations and our responses to them.

1. Why use THC instead of marijuana? We have chosen to develop the app tasks with THC because the drug is readily available and because it has a known pharmacology, time course and dose effects. We recognize that we propose to use the app in a naturalistic setting where users will be using marijuana, and not THC, and where we have little control of the composition of the marijuana they will be using. However, to develop a task sensitive to the primary psychoactive ingredient of marijuana, we feel that oral THC is the drug with which we have the most control.
2. Why not obtain plasma samples of THC and its metabolites during each session, to link impairments to plasma levels of THC and its metabolites? This would be extremely valuable, and we have given careful consideration to the possibility of obtaining plasma samples. It would help to account for individual differences in absorption and metabolism, and to serve as a comparison to drug levels

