Selection of tasks: We have selected five app tasks from ResearchKit [<http://www.researchkit.org/docs/docs/ActiveTasks/ActiveTasks.html>] that are likely to be affected by marijuana (Broyd et al, 2016; Hartman and Huestis, 2013). These are spatial-span memory), finger tapping, reaction time, mental addition, and time perception/estimation. These tasks assess basic motor, psychological and cognitive function that THC and marijuana are known to affect (Broyd et al, 2016; Hartman and Huestis, 2013; Sewell et al. 2013). The tasks are relevant to everyday activities including safe operation of machines and accurate decision-making in a job setting. Note that the App to be used in the future naturalistic study will include additional features related to consent, demographic characteristics and data collection and management. However, for the present, laboratory-based study we will only use the App to administer the tasks and collect data on the hand-held device. We have selected four tasks from ResearchKit for initial testing, with the goal of selecting the three most sensitive tasks for the next stage of the project. The working software operates on a mobile device using Apple's ResearchKit framework. For the purpose of this laboratory-based preliminary study we will distribute the app to iOS devices we provide through the Apple "B2B" (business-to-business) distribution system. Reviewers wishing to examine the app should ask us for a redemption code that will give them access. Task performance and questionnaire data collected on the app will be transferred to an Access database on our main computer system.

The four tasks will be presented in mixed order at each hourly administration of the task. From these four tasks we propose to select the three tasks that are most sensitive to the effects of THC, and show the least change in learning across sessions.

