- Spatial Memory (forward and reverse): In this memory task participants are asked to observe and then recall pattern sequences of increasing length in a game-like environment. The span is automatically varied during the task, increasing after successful completion of a sequence, and decreasing after failures, in a range from 3 to 9. The play speed is set at 1.0 second and the custom target image is the flower. The game finishes when either 7 tests have been completed, or the participant has made two consecutive failures in a row. In the reverse portion of the task participants must recall pattern sequences in reverse order.
- Finger-tapping: In this measure of psychomotor performance and coordination, the participant rapidly alternates between tapping to targets on the touch screen using the non-dominant hand for 20 seconds.
- Reaction time: In this reaction time task, the user is asked to shake the device in response to a visual

clue on the device's screen. The user makes three attempts, in which he or she must shake or move the device with an acceleration that is greater than the value of the thresholdAcceleration property within the given time. The task finishes when the user successfully completes the attempts as instructed in the task. Data collected by this task is in the form of `ORKReactionTimeResult` objects. Each of these objects contain a timestamp representing the delivery of the stimulus and an `ORKFileResult` object that references the motion data collected during an attempt.

- Paced Visual Serial Addition Task (PVSAT). The PVSAT measures cognitive function that assesses visual information processing speed, flexibility, and the calculation ability of the user. Single digits are presented every 2 or 3 seconds and the user must add each new digit to the one immediately before. The score for the PSAT task is the total number correct answers out of the number of possible correct answers.
- Time Perception/Estimation Task. The time perception/estimation task measures two components of time perception, time estimation as well as time production. The user must estimate the amount of time elapsed during a certain visual distraction for several trials and then the user must hold down a button for a defined period of seconds without seeing a timer.

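### The app reaction-time task has three attempts, a success-based ending and no score or rule for failed attempts, so a THC effect may be attenuated or imprecisely measured

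*Combined protocol and SAP*

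**What the plan says.** All references are to the combined protocol and SAP.

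- **Task (Dependent measures, Reaction time).** "The user makes three attempts, in which he or she must shake or move the device" with an acceleration "greater than the value of the thresholdAcceleration property within the given time". Neither the threshold nor the time limit is given a value.
- **Ending rule (same item).** "The task finishes when the user successfully completes the attempts as instructed in the task". What happens after a failed attempt is not described.
- **Data kept (same item).** The result objects "contain a timestamp representing the delivery of the stimulus and an `ORKFileResult` object that references the motion data collected during an attempt". No summary score follows.
- **Contrast within the section.** The serial addition task has a score in which misses count: "The score for the PSAT task is the total number correct answers out of the number of possible correct answers". The spatial memory task stops after a set number of tests or two failures in a row, so failures enter its ending rule.
- **Use of the result.** Data analysis and timeline makes app-task performance a primary outcome. Its data-quality exclusion covers only grossly inappropriate responses. Selection of tasks says "From these four tasks we propose to select the three tasks that are most sensitive to the effects of THC", with little learning across sessions as the other criterion.
- **Expected drug effect (Approach).** THC "is known to impair short-term memory, increase reaction time and impair attention".
- **Timing.** Aim 1, Approach and Experimental protocol place the app tasks 2 hours after the capsule. Selection of tasks speaks of hourly administrations.

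**The concern.** There are two separate problems.

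**Bias.** If an attempt that misses the limit or the threshold is simply repeated until it succeeds, and only successes are scored, the score is conditional on success. The plan itself expects THC to slow responses and impair attention, so failures should be commoner on THC. Removing them trims more from the THC sessions than from the placebo sessions and pulls the difference toward zero.

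**Precision.** Three responses per run make a short sample of a variable quantity, even if every response is scored.

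Reaction time competes with the other tasks for a place in the field app. Either problem could cost it that place because of how it was configured, and not because THC leaves reaction time unaffected. The desktop version is to be a conversion of the same task, so it may carry the same features into the app-desktop comparison.

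**Working it through.** **1. The plan's own figure.** Sample Size and Power gives 48 completers without alpha, power, or a reaction-time effect or SD, so 48 cannot be reproduced. The only quantified effects are for memory of affective images: partial eta squared 0.13 and 0.20. With dz = √(η²/(1−η²)):
- √(0.13/0.87) = 0.387, giving about 75% power with 48 at two-sided 0.05 (paired t test)
- √(0.20/0.80) = 0.50, giving about 92%

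Neither concerns reaction time. With 48 completers, 80% power needs dz = 0.413.

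**2. Precision with k attempts.** If every attempt is scored by its mean, the SD of the THC-minus-placebo difference is √(2 × (session SD² + trial SD²/k)), and dz is the effect divided by that SD. The documents give none of these inputs. Assumed: effect 30 ms, trial SD 80-200 ms, session SD 20-40 ms.

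Best case, trial SD 80 and session SD 20:
- k = 3: √(2 × (400 + 2133)) = 71.2 ms; dz = 30/71.2 = 0.42
- k = 20: √(2 × (400 + 320)) = 37.9 ms; dz = 0.79

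Worst case, trial SD 200 and session SD 40:
- k = 3: √(2 × (1600 + 13333)) = 172.8 ms; dz = 0.17
- k = 20: √(2 × (1600 + 2000)) = 84.9 ms; dz = 0.35

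| Trial SD / session SD (ms) | dz, 3 attempts | Power | dz, 20 attempts | Power |
|---|---|---|---|---|
| 80 / 20 | 0.42 | 82% | 0.79 | >99% |
| 80 / 40 | 0.35 | 65% | 0.48 | 91% |
| 120 / 20 | 0.29 | 52% | 0.63 | 99% |
| 120 / 40 | 0.27 | 44% | 0.44 | 85% |
| 200 / 20 | 0.18 | 23% | 0.43 | 84% |
| 200 / 40 | 0.17 | 22% | 0.35 | 67% |

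The assumed effect matters as much as the SDs. With three attempts over the same grid, a 50 ms effect has power from 50% to over 99%, and a 100 ms effect about 98% or more throughout.

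**3. Bias if failures are repeated and dropped.** Simulation with 48 subjects, three attempts and 4,000 replicates. Response times are a normal component plus an exponential one. Placebo: normal mean 350 ms, SD 50 ms, exponential mean 100 ms. THC adds 20 ms to the normal mean and 30 ms to the exponential mean, a true effect of 50 ms. Between-subject SD is 40 ms and session SD 20 ms. Responses over the limit are redrawn until one succeeds. All values are assumed.

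| Time limit | Missed, placebo / THC | Measured effect | SD of difference | Power |
|---|---|---|---|---|
| Every attempt scored | n/a | 50 ms | 106 ms | 90% |
| 600 ms | 10% / 20% | 24 ms | 64 ms | 70% |
| 700 ms | 4% / 9% | 32 ms | 78 ms | 78% |
| 800 ms | 1.4% / 4.2% | 38 ms | 88 ms | 83% |
| 1000 ms | 0.2% / 0.9% | 46 ms | 100 ms | 88% |
| 2000 ms | about 0 / 0 | 50 ms | 106 ms | 89% |

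Closed-form check of the first row: trial variances are 50² + 100² = 12,500 and 50² + 130² = 19,400, so the SD is √(2 × 400 + 31,900/3) = 107 ms, in line with the simulated 106.

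Dropping failures shrinks the effect and also the SD. The loss of power therefore comes from attenuation, and any imprecision comes from the small number of attempts.

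**The case against.** A reader might infer that slow and missed responses are definitely replayed and never scored. The documents do not say so. They describe three attempts, a success-worded ending and motion data stored for each attempt. Repetition is one reasonable reading. A slow response inside the limit succeeds and is recorded under any reading; only responses past the limit, absent or too weak could be lost.

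A reader might also infer that the measure is too noisy to show a THC effect. That does not follow either: the power range in the working runs from poor to ample, and the inputs that decide it are not in the documents. Nor do the documents give failure rates from which to say how well a failure count would perform.

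Two further points are fair. If the tasks run hourly, as Selection of tasks suggests, a session holds more than three attempts; this would help precision but would not remove the bias. And this is a proof-of-concept study choosing brief tasks as built, so rejecting an insensitive one is a legitimate result.

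The planned look at the first 8 participants (Possible pitfalls) does not settle the matter. In the 30 ms, three-attempt grid, power with 8 participants is 7-18%. A task changed at that point would leave the early participants on a different version, and raising difficulty does not define how failures are scored.

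What stands is that a primary-outcome task has neither a score nor a rule for failed attempts, and that its length can be improved at little cost.

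**Conclusion.** The concern holds in a conditional form; it is a cheap improvement. What is certain from the text is three attempts per run, a success-based ending, no score, no failure rule, and no stated limit or threshold. If failed attempts are dropped and THC increases them, the drug effect is biased toward zero. Under the assumed response times the measured share of a 50 ms effect is about half at a 600 ms limit (24/50), about three quarters at 800 ms (38/50), and all of it at 2000 ms. Separately, three attempts give dz of about 0.17-0.42 for an assumed 30 ms effect, against 0.35-0.79 with 20. Five of the six scenarios fall below 80% power with three attempts and one of six with 20. Every reaction-time effect, SD and limit here is an assumption. A large effect would be found either way.

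**What to change.** Before the first participant, in the Reaction time item under Dependent measures and for the desktop version:

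1. Set a fixed number of stimuli, for example 15-20, and end the task after that number whether or not each response succeeds.
2. Record every attempt, including late, missed and too-weak responses.
3. Define the score as the median response time with failed attempts ranked as slowest (or treated as censored at the stated limit), and report the count of failed attempts beside it.
4. State the time limit and the acceleration threshold, and keep both the same for all sessions.
5. Reconcile the 2-hour timing in Aim 1, Approach and Experimental protocol with the hourly administration in Selection of tasks, so that the number of attempts per session is known.

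The cost is a task setting, a scoring paragraph and an estimated 1-2 extra minutes per run, in a 4-hour session that already has free time. The price is a slightly less brief app task. The number of stimuli is a suggestion; an estimate of trial-to-trial SD from practice runs at the orientation session would let the investigators set it on evidence.

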Innovation. This project is highly innovative in several respects. The ultimate goal is to develop an app that will enable users' to assess their level of impairment in the own natural environments. The app-based tasks will be brief, simple and sensitive, and relate to impairments that may affect the user's functioning. The app will also provide unique new information about the extent to which users are aware of their impairments in performance. The project outlined here is the first step to developing this app, by testing it in a controlled setting.

Approach.

This is a proposal for an administrative supplement to obtain preliminary, proof-of-concept data to **develop an app for self-assessment of cannabis-induced impairment**. Marijuana use, for both recreational and therapeutic purposes, is becoming increasingly common as states remove restrictions on use. The increased use raises new concern about the safety of this drug, including its ability to impair basic cognitive and psychomotor tasks, and whether the users are aware of their impairment.

We propose to design a simple performance test that users can use in the field, using a cell phone, to assess their level of impairment *relative to their own drug-free state*. In this preliminary study we will compare participants' simple task performance after a known dose of delta-9-tetrahydrocannabinol (THC), or placebo, administered under double blind conditions. In our app the participants will be asked to gauge their own perceived level of impairment (as determined by self-ratings and judgments of impairment) as well as their actual impairment (as gauged by the app), providing important feedback and training about their ability to detect impairment. In the ultimate version of the app (though not in this task development study) we will provide participants with feedback about their performance, including both their objective performance and their perceptions of the performance. It will be valuable for users to know that their drug use leads to decrements in performance, and it would be especially informative if we can demonstrate their inability to gauge their own impairment. These features will be part of the final app, when we get to the point of administering it repeatedly in the non-laboratory setting.

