Experimental protocol. Each subject will participate in three sessions (0, 7.5 mg and 15 mg THC) in counterbalanced order, separated by at least one week. The sessions will be conducted from 9 am to 1 pm. Upon arrival in the laboratory for each session subjects will provide urine samples to rule out recent use of opiates, stimulants, sedatives, cannabinoids, and breath samples for recent alcohol use and urine samples to test for pregnancy (women). Those who test positive for any drugs will be rescheduled and pregnant women will be dropped. Participants will then complete pre-drug mood questionnaires and their heart rate and blood pressure will be measured. They will then ingest a capsule containing 0, 7.5 or 15 mg Dronabinol with 100 ml water. One drug condition will be administered on each of the three days, in mixed order and under double-blind conditions. Subjects will complete the tasks 2 hours after ingesting the capsule, and heart rate and blood pressure, as well as mood questionnaires, will be measured at half hour intervals. At times when no experimental events are scheduled subjects will be free to relax, read or watch tv. Following the sessions subjects will be escorted to public transportation or provided with transportation home.

Drug. THC (Marinol® [dronabinol]; Solvay Pharmaceuticals) will be orally administered in doses of 7.5 mg and 15 mg, in opaque capsules with dextrose filler. Placebo capsules contain only dextrose. These doses of THC are known to produce performance impairments as well as subjective intoxication (Broyd et al, 2016; Hartman and Huestis, 2013).

Dependent measures.

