Self-evaluations of performance on the app tasks. Subjects will be asked to estimate their performance on the tasks immediately before and following each task. They will indicate on a 5-point scale whether they think their performance will be or was poorer than normal (1-2), about the same as normal (3) or better than normal (4-5). They will not be provided with feedback on their estimates, relative to their actual performance, until the end of the study. The apps are currently being developed.

Computer-based tasks. Participants will also complete standardized psychomotor tasks on a desktop computer 1.5 hours after drug administration. We will be converting all the ResearchKit tasks into computer-based tasks. This will allow us to compare performance decrements using the hand-held device to impairments seen with typical laboratory tasks.

Self-report rating questionnaires. Prior to performing the tasks as well as after completing the tasks, they will also complete questionnaires regarding the mood and intoxication states 0, 1.5, 1, 1.5, 2, 2.5, and 4 hours after consumption. They will complete the Drug Effects Questionnaire (Morean et al 2013), asking whether they feel a drug effect, whether they like or dislike it and whether they feel high. They will also complete a shortened version of the Marijuana scale of the Addiction Research Center Inventory (Chait et al 1994) to detect marijuana-specific mood effects.

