Data analysis and timeline. The primary outcome measures are i) actual performance on the app tasks; ii) actual performance on the desktop tasks. iii) predicted and perceived performance on each task, and iv) ratings of how "high" the subject feels. First we will examine the quality of the data to exclude grossly inappropriate responses (e.g., all minimum or all maximum values). Then we will determine whether there are orderly changes in task performance (i.e., improvement or decline) across the 3 sessions, and co-vary for session order if necessary. Then we will assess the effects of the drug on performance on each task and on the mood questionnaires using linear mixed models for repeated measures (Hedeker & Gibbons, 2006) with factors of drug condition and session time point, and random subject intercept and session effects. For drug condition, we will treat placebo as the reference cell and make comparisons of each drug level to placebo. We expect that the effects of THC on both subjective state and performance will peak two hours after drug ingestion. Finally, we will examine relationships across variables. We will examine the concordance in impairment using the desktop administered tasks and the tasks administered with hand-held devices. We will also examine the relationship between participants' estimates of the impairment and their actual impairment by calculating a ratio between the two (drug minus placebo for estimates: drug minus placebo for actual impairment). We expect that it will take one year to complete testing of 48 participants in the three sessions, and to conduct the analyses of the findings. Our goal is to have a fully functional and sensitive app ready to test in a non-laboratory, naturalistic setting.

Possible pitfalls. It is possible that the tasks, either app-based or computer based, will fail to detect THC-induced impairments. We will examine data from completed subjects as we go, and if we fail to see

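### The data-quality screen gives all-minimum or all-maximum values as its only example; applied to 'high' or self-evaluation ratings, it could remove true answers and bias the contrasts with placebo

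*Combined protocol and SAP*

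**What the plan says.** The section Data analysis and timeline names four primary outcomes: performance on the app tasks, performance on the desktop tasks, "iii) predicted and perceived performance on each task, and iv) ratings of how" high the participant feels. The next sentence is the screen: "First we will examine the quality of the data to exclude grossly inappropriate responses (e.g., all minimum or all maximum values"). The mixed models follow, and for these "For drug condition, we will treat placebo as the reference cell and make comparisons of each drug level to placebo".

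The following passages bear on what a rating at the scale limit means:

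- Under Drug: "Placebo capsules contain only dextrose".
- Under Experimental protocol, on the urine and breath tests at arrival: "Those who test positive for any drugs will be rescheduled".
- Under Self-report rating questionnaires, the drug-effect questionnaire is described as "asking whether they feel a drug effect, whether they like or dislike it and whether they feel high". Its scale range is not given.
- Under Self-evaluations of performance on the app tasks, participants rate each task before and after doing it on a 5-point scale, where 1 and 2 are worse than normal, 3 is normal, and 4 and 5 are better.
- Aim 2 is about whether participants can predict and judge their own impairment.

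Nothing else in the document defines the screen. Double-blind conditions are stated for drug administration only.

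**The concern.** A data-quality screen should remove records that are not real measurements. The only criterion offered here is the value of the outcome itself. For two of the four primary outcomes, that criterion can describe an honest answer.

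- **'High' ratings.** A participant who arrives drug-free and receives dextrose may well report the minimum throughout the session. Removing such sessions takes low values out of the reference cell for every contrast.
- **Self-evaluations.** Uniform 1s after THC may be true awareness of impairment, and uniform 5s may be true overconfidence. Both are what Aim 2 sets out to measure. The ratings also feed the planned ratio ("drug minus placebo for estimates: drug minus placebo for actual impairment").

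In both cases exclusion would depend on the outcome and probably on dose. The planned mixed model does not correct for that kind of loss. Because the unit of 'all' is open (items, time points, a session, every session), two analysts following the text could report different results. The plan does not commit to reporting what was removed.

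**Working it through.** The plan attaches no figure to this rule, so there is none to reproduce. The check asks what happens to the contrasts if the example is applied. The 48 participants, three conditions and 5-point scale come from the documents. **Every rate, mean and SD below is an assumption.**

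**1. 'High', whole sessions excluded.** Let p and q be the shares of all-minimum sessions on placebo and at 15 mg. Let m0 and m1 be the mean ratings in the remaining sessions, measured from the scale minimum, and k = m0/m1.

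- Before exclusion: m1(1-q) - m0(1-p)
- After exclusion: m1 - m0
- After/before = (1-k) / [(1-q) - k(1-p)]

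The contrast shrinks only if q < kp, and grows if q > kp. With m0 = 15 and m1 = 45 (k = 1/3), the contrast after exclusion is always 30:

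| p | q | Before | After | Change |
|---|---|---|---|---|
| 30% | 0 | 34.5 | 30 | -13% |
| 50% | 0 | 37.5 | 30 | -20% |
| 70% | 0 | 40.5 | 30 | -26% |
| 30% | 10% | 30 | 30 | 0 |
| 50% | 10% | 33 | 30 | -9% |
| 70% | 10% | 36 | 30 | -17% |
| 50% | 30% | 24 | 30 | +25% |

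With p = 50% and q = 0, k = 0.1 gives 0.9/0.95 (-5%) and k = 0.5 gives 0.5/0.75 (-33%).

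**2. 'High', only participants at the minimum in every session excluded.** They contribute zero in each condition, so after = before/(1-r), where r is their share. Such a participant is also at the minimum at 15 mg, so r cannot exceed q. With p = 50% and q = 10%, r is at most 10% and the contrast rises at most from 33 to 33/0.9 = 36.7 (+11%). Session-level exclusion under the same rates lowers it by 9%. The two readings of 'all' therefore move the estimate in opposite directions.

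**3. 'High', simulated mixed models, 48 participants.**

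- One score per session on an assumed 0-100 scale, cut off at zero, SD 12 between and 12 within participants. With 28%, 50% and 68% of placebo sessions at the minimum, against 2-4% at 15 mg, the 15 mg contrast goes from 22.1 to 19.4, 23.7 to 20.8 and 26.6 to 23.8 (11-12% smaller). The 7.5 mg contrast goes from 7.9 to 6.7, 10.3 to 9.5 and 10.9 to 10.4, also smaller.
- Ratings at the six distinct listed times, also cut off at zero, with 61-65%, 18-26% and 1-5% all-minimum sessions at 0, 7.5 and 15 mg. At 2 hours the 7.5 mg contrast rises from 10.0 to 11.4 or 12.3 (+14% or +23%), while the 15 mg contrast moves only from 28.2 to 28.0 or from 27.0 to 27.5 (-1% or +2%).

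Two reasonable models thus disagree on the sign at 7.5 mg, and one finds almost no effect at 15 mg. The exact percentages also shift with the way the variance components are estimated.

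**4. Self-evaluations.** Assume a placebo mean of 3 and a mean of 2.5 in the other 15 mg sessions, so D = -0.5, and let s be the share of 15 mg sessions with uniform answers. Before = (1-s)D - 2s for uniform 1s, or (1-s)D + 2s for uniform 5s. After = D.

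| Uniform answer | s | Before | After | Change in size |
|---|---|---|---|---|
| 1 | 5% | -0.575 | -0.5 | -13% |
| 1 | 10% | -0.65 | -0.5 | -23% |
| 5 | 5% | -0.375 | -0.5 | +33% |
| 5 | 10% | -0.25 | -0.5 | +100% |

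Five and ten per cent of 48 sessions is about 2 and 5 sessions.

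**The case against.** The strongest reply is that the operative test is whether a response is grossly inappropriate, and that the extreme values are only an example. A sensible analyst would not call a minimum 'high' rating after dextrose inappropriate. That stands. A reader might infer that the plan will delete true placebo answers, but the documents do not show it. They show a stated example that gives a worse result if followed, and no text that stops it being followed.

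A reader might also infer that the THC effect on 'high' would be understated. The documents do not support that either. The rule would drop all-minimum THC sessions too, the direction turns on whether q < kp, and no floor rates are given. Large inflation from participant-level exclusion (+25% at r = 20%) would need at least 20% all-minimum sessions at 15 mg. That sits poorly with the statement under Drug that these doses are known to cause subjective intoxication.

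Self-evaluations are less exposed. The expected placebo answer is 3, which the screen does not touch. With two ratings for each of four or five tasks (Selection of tasks gives both counts), a uniform session means 8 to 10 identical extreme ratings. The 5-10% rates are assumed. The remark under Approach that "it would be especially informative if we can demonstrate their inability to gauge their own impairment" comes in a discussion of the finished app, so Aim 2 is the firmer anchor.

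Finally, keeping every uniform rating is not harmless. If the uniform 5s in the table were careless, retaining them would pull -0.5 to -0.375 or -0.25, an attenuation of 25-50%. That argues for a defined invalidity rule and a comparison with and without exclusions. It does not support a rule based on the value alone. No harm is shown for actual task performance, the study's primary goal.

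**Conclusion.** The concern holds in conditional form. If the plan's only stated example is applied to 'high' or self-evaluation ratings, exclusion depends on the outcome and probably on dose, and the contrasts with placebo can be biased. The case is strongest for 'high', where an all-minimum placebo session is a plausible true answer in the reference cell. It is weaker for self-evaluations, where it rests on Aim 2.

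Direction and size cannot be fixed from the documents. For 'high' at 15 mg, the session-level illustrations run from -33% to +25%, and the bias may be negligible. All of them rest on assumed floor rates and means. This should be fixed before analysis because the step precedes the models for all four primary outcomes and the remedy is cheap. It is not evidence that the planned results will be biased.

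**What to change.** Replace the sentence with a short paragraph that does the following:

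- States that a value at the scale limit is not by itself a reason to exclude 'high', other drug-effect or self-evaluation ratings.
- Allows exclusion only on evidence of invalidity: device failure, task not attempted, an impossible value, or a pre-defined straight-lining rule across items where uniform answers are implausible.
- Defines the unit of exclusion for each outcome.
- Has the decisions made without treatment codes.
- Reports exclusions by dose and outcome, and repeats the primary contrasts with all data.

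The cost is one paragraph and one repeat analysis. The downside is that some careless responders may be kept, which can add noise or some bias. Setting the results with and without exclusions side by side would show how much that matters.
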